10.3 Stopping Rules and Data Safety Monitoring

A Data Safety and Monitoring Board (DSMB) appointed by the NHLBI Division of Intramural Research will monitor the safety of subjects in the study as described in the investigational plan. All members of the DSMB are unaffiliated to the study. The NHLBI DSMB will review the protocol progress report at sixmonth intervals. The DSMB may recommend early termination of the study for considerations of safety and efficacy. Unanticipated Adverse Device Effects (UADEs) will be submitted to the DSMB following the same timelines as the IRB (See section 9.2.4).

In the case of death or serious UADE, if the sponsor and the principal investigator determine that the event presents an unreasonable risk to the participating subjects, the clinical trial will be terminated within 5 working days after making that determination and not later than 15 working days after the sponsor first receives notice of the effect. [21 CFR 812.46]. All clinical sites will be notified of this action.

Each institutional IRB will review all Serious Adverse Events, Unanticipated Adverse Device Effects, and Unanticipated Problems, and may choose to suspend or terminate the protocol based on those findings. We believe this will protect subject safety.

Stopping rules were changed in Amendment A to be more statistically robust, to accommodate two strata of patients, and to focus on 30-day survival. There are two clearly different strata of subjects to be enrolled in this study. For TMVR in the setting of prior annuloplasty (aka "valve-in-ring" or "valve-in-band"), the risk of valve migration and of severe paravalvular leak, attendant mortality, are much lower. For TMVR in the setting of mitral annular calcification (aka "valve-in-MAC"), patients are older and have more comorbidity, and the procedures are much more technically complex. Accordingly, valve-in-MAC TMVR has higher mortality. The reported 30-day mortality of valve-in-MAC in the global registry of 64 patients was $30\%^{14}$.

We propose two different stopping rules, one for valve-in-ring and valve-in-band, and another for valve-in-MAC. While rules are provided for up to 30 subjects in each stratum, the total treated within both strata combined will not exceed 30.

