10.0 BIOSTATISTICAL AND ANALYTICAL CONSIDERATIONS

10.1 Sample Size

The sample size is not statistically derived. This is a safety and feasibility study that enables patient access to off-label use of a medical device, when these patients have no other good medical options to treat

symptomatic mitral valve failure. An arbitrary initial sample size of 30 is proposed, and will be increased if needed, until a commercial solution is found for medical care.

Up to 60 subjects will be consented until 30 subjects undergo attempted LAMPOON TMVR in this protocol.

We will adhere to the extent possible to consensus guidelines that have been established for the analysis and reporting of transcatheter mitral valve repair investigational procedures. 19, 20

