10.3.1 Stopping Rules for valve-in-ring and for valve-in-band stratum

The study will be monitored to ensure that the mortality with 30-days after the procedure does not substantially exceed an anticipated rate. We anticipate the rate of 30-day mortality is 10% or less and determine the stopping rule by a Bayesian approach 25 . The stopping boundary is reached if the posterior probability that the 30-day mortality rate exceeds 10% is at least 90%. We take our prior distribution to be a beta distribution so that our prior clinical opinion is worth 20% of the weight we will place on the new study data, which gives the prior parameters a = 0.6, b = 5.4. Hence when we make decisions about stopping the study, the data from the study will dominate over the prior opinion.

The following table summarizes the threshold numbers for the stop rule boundary, which would lead to a recommendation to stop the study due to the excess 30-day mortality.

Number of subjects in the stratum	Stop if the number of deaths within 30 days reaches
2-4	2
5-10	3
11-17	4
18-24	5
25-30	6

We investigated the performance of the above stopping rule by a simulation study. In each simulation run, we generated a study with 30 independent Bernoulli trials, each with a true certain 30-day mortality, and compared these outcomes with the above stopping boundary to determine whether the study was stopped. We repeated the simulation 100,000 times and computed the proportion of stopped studies using the above stopping rule. The following table summarizes the performance of this stopping rule:

True 30-day mortality rate	5%	10%	15%	20%	25%	30%	35%	40%
Proportion of Stopped Studies	2.9%	16.9%	42.1%	68.7%	86.0%	94.9%	98.6%	99.7%
Average number of subjects	29.4	27	22.8	17.9	13.8	10.6	8.2	6.6
Average number of 30-day mortality	1.5	2.7	3.4	3.6	3.4	3.2	2.9	2.7

These simulation results suggest that our stopping rule has a low probability stopping a study when the true 30-day mortality rate is 10% or less, and the probability of stopping a study is high when the true 30-day mortality rate exceeds 10%. There, we believe that our Bayesian stopping rule for 30-day mortality has satisfactory statistical properties.

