10.3.2 Stopping Rules for valve-in-MAC stratum

The study will be monitored to ensure that the mortality with 30-days after the procedure does not substantially exceed an anticipated rate. We anticipate the rate of 30-day mortality is 30% or less and determine the stopping rule by a Bayesian approach 25 . The stopping boundary is reached if the posterior probability that the 30-day mortality rate exceeds 30% is at least 90%. We take our prior distribution to be a beta distribution so that our prior clinical opinion is worth 20% of the weight we will place on the new data. This gives the prior parameters a = 1.8, b = 4.2. Hence when we make decisions about stopping the study, the data from the study will dominate over the prior opinion.

The following table summarizes the threshold numbers for the stop rule boundary, which would lead to a recommendation to stop the study due to the excess 30-day mortality.

Number of subjects in the "valve-in- MAC" stratum	Stop if the number of deaths within 30 days reaches
3	3
4-6	4
7-8	5
9-11	6
12-14	7
15-16	8
17-19	9
20-22	10
23-25	11
26-27	12
28-30	13

We investigated the performance of the above stopping rule by a simulation study. In each simulation run, we generated a study with 30 independent Bernoulli trials, each with a true certain 30-day mortality, and compared these outcomes with the above stopping boundary to determine whether the study was stopped. We repeated the simulation 100,000 times and computed the proportion of stopped studies using the above stopping rule. The following table summarizes the performance of this stopping rule:

True 30-day mortality rate	20%	25%	30%	35%	40%	45%	50%	55%
Proportion of Stopped Studies (%)	3.9	10.2	21.8	38.9	58.5	76.6	89.1	95.9
Average number of subjects	29.2	28.1	26.1	23.3	20	16.4	13.2	10.5
Average number of 30-day mortality	5.8	7	7.8	8.2	8	7.4	6.6	5.8

These simulation results suggest that our stopping rule has a low probability stopping a study when the true 30-day mortality rate is 30% or less, and the probability of stopping a study is high when the true 30-day mortality rate exceeds 30%. There, we believe that our Bayesian stopping rule for 30-day mortality has satisfactory statistical properties.

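### Both stopping-rule performance tables assume 30 subjects in the stratum, but the two strata share one cap of 30, so the stated chance of stopping is too high in at least one stratum

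*Combined protocol and SAP*

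**What the plan says.** Section 10.3 divides subjects into two strata, prior annuloplasty (ring or band) and mitral annular calcification (MAC), and gives each its own rule. On numbers it says: "While rules are provided for up to 30 subjects in each stratum, the total treated within both strata combined will not exceed 30".

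Sections 10.3.1 and 10.3.2 then report how each rule performs. Both describe the simulation in the same terms: "we generated a study with 30 independent Bernoulli trials, each with a true certain 30-day mortality". Each section concludes from its table that its rule is statistically satisfactory. Section 10.3.1 says "the probability of stopping a study is high when the true 30-day mortality rate exceeds 10" per cent; Section 10.3.2 says "the probability of stopping a study is high when the true 30-day mortality rate exceeds 30" per cent. On the prior, Section 10.3.1 says "our prior clinical opinion is worth 20% of the weight we will place on the new study data", and Section 10.3.2 makes the same statement. Crossing a boundary is an event "which would lead to a recommendation to stop the study due to the excess 30-day mortality", that is, the whole study and not only the stratum.

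Section 10.1 describes the sample size differently: "An arbitrary initial sample size of 30 is proposed, and will be increased if needed".

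**The concern.** The tables are the only evidence offered that the rules protect subjects adequately, and both rest on a stratum size that the cap does not allow once both strata enrol. The printed averages show the conflict. At the anticipated rates (10% ring/band, 30% MAC) they imply 27 + 26.1 = 53.1 subjects and 2.7 + 7.8 = 10.5 deaths, against a cap of 30 subjects.

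A smaller stratum gives the rule fewer chances to fire. A DSMB, IRB or regulator reading the tables would therefore expect a higher chance of stopping under excess mortality than at least one stratum can deliver. What is at stake is the stated level of protection. No boundary is wrong.

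**Working it through.** **Inputs.** From 10.3.1: prior Beta(0.6, 5.4), reference rate p0 = 10%. From 10.3.2: prior Beta(1.8, 4.2), p0 = 30%. Both stop when the posterior probability that mortality exceeds p0 is at least 90%. From 10.3: combined cap of 30. The split between strata is not given, so results are shown by stratum size.

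**Step 1: boundaries.** For n subjects, find the smallest d with P(p > p0 | Beta(a + d, b + n − d)) ≥ 0.90. This matches both printed boundary tables at every n from 1 to 30.

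**Step 2: the plan's own performance figures.** An exact recursion over the number of deaths, checking the boundary after each subject up to N = 30, gives:

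- Ring/band at 5, 10, 15, 20, 25, 30, 35, 40%: 2.8, 17.1, 42.6, 68.3, 86.0, 95.0, 98.5, 99.7%. Printed: 2.9, 16.9, 42.1, 68.7, 86.0, 94.9, 98.6, 99.7%.
- MAC at 20, 25, 30, 35, 40, 45, 50, 55%: 3.8, 10.1, 21.8, 38.9, 58.6, 76.4, 89.0, 95.9%. Printed: 3.9, 10.2, 21.8, 38.9, 58.5, 76.6, 89.1, 95.9%.

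All 16 agree within 0.5 point, so the tables are right for a full 30 in one stratum.

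**Step 3: the same recursion at N = 15 (assumed 15/15 split).**

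| Ring/band true mortality | Printed | N = 15 | Gap (points) |
|---|---|---|---|
| 10% | 16.9 | 11.3 | 5.6 |
| 15% | 42.1 | 26.6 | 15.5 |
| 20% | 68.7 | 44.7 | 24.0 |
| 25% | 86.0 | 62.2 | 23.8 |
| 30% | 94.9 | 76.4 | 18.5 |
| 35% | 98.6 | 86.7 | 11.9 |
| 40% | 99.7 | 93.2 | 6.5 |

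| MAC true mortality | Printed | N = 15 | Gap (points) |
|---|---|---|---|
| 30% | 21.8 | 15.2 | 6.6 |
| 35% | 38.9 | 25.7 | 13.2 |
| 40% | 58.5 | 38.8 | 19.7 |
| 45% | 76.6 | 53.0 | 23.6 |
| 50% | 89.1 | 66.9 | 22.2 |
| 55% | 95.9 | 78.8 | 17.1 |

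Below the anticipated rates the gap is small: 0.6 point (ring/band at 5%), and 0.6 and 2.4 points (MAC at 20% and 25%).

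**Step 4: other stratum sizes.** Range of printed minus exact over the excess rates (ring/band 15–40%, MAC 35–55%):

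| Stratum size | Ring/band | MAC |
|---|---|---|
| 25 | 0.7–6.3 | 2.3–4.8 |
| 20 | 2.5–15.0 | 8.6–14.7 |
| 15 | 6.5–24.0 | 13.2–23.6 |
| 10 | 14.8–34.8 | 21.5–40.6 |
| 5 | 31.1–60.1 | 31.7–67.2 |

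For every size from 1 to 15, the largest gap is at least 23.6 points in either table.

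**Step 5: study-level stopping, which the plan does not report.** With independent strata, P(either boundary) = 1 − (1 − P_ring)(1 − P_MAC). At the anticipated rates:

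- 20 ring/band and 10 MAC: 1 − (0.864)(0.895), about 22.6%.
- 15 and 15: 1 − (0.887)(0.848) = 24.8%.
- 10 and 20: 1 − (0.904)(0.825), about 25.5%.

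All three exceed the printed single-stratum figures of 16.9% and 21.8%.

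**Step 6: the two related statements.**

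- *High chance of stopping.* Even with 30 subjects, the printed chance is 42.1% at 15% (ring/band) and 38.9% at 35% (MAC). Both are below one half although mortality exceeds the anticipated rate.
- *Weight of the prior.* 0.6 + 5.4 = 6 and 1.8 + 4.2 = 6 pseudo-subjects. 6/30 = 20%, but 6/15 = 40%. The stated weight again presumes a full 30 in the stratum.

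**The case against.** The strongest reply is that nothing is miscalculated. Each table is right for the 30 subjects it says it simulates, and the cap is disclosed just before. That is so, but the cap is not carried into the tables. No figure is given for a smaller stratum, and the conclusions rest on the tables as printed.

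The second reply is that reaching either boundary stops the study, so the study-level chance is what counts. At 15/15 with both strata in excess, it is 45.5% at 15%/35%, 66.2% at 20%/40% and 82.2% at 25%/45% (ring/band/MAC), which lies between the two printed figures or above both. This stands: when both strata are in excess, the printed figures roughly describe the chance of stopping. It fails when only one is. At 15/15 with ring/band at 20% and MAC at its anticipated 30%, the chance is 1 − (0.553)(0.848) = 53.1%, against 68.7% printed. With ring/band at 10% and MAC at 45%, it is 1 − (0.887)(0.470), about 58%, against 76.6%.

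Other points stand in part:

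- The split is an assumption, and a stratum of 25 is close to its table; the other stratum then has 5 and is far from its own.
- A smaller stratum also has fewer expected deaths than printed: 2.3 against 3.6 for ring/band at 20%, and 5.0 against 7.4 for MAC at 45%, both at n = 15.
- The data still outweigh the prior at 15 against 6.
- If the sample may grow, as Section 10.1 allows, a stratum could reach 30, but that contradicts the cap in 10.3.
- DSMB review every six months, IRB review of serious events and the sponsor's power to terminate all remain.

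**Conclusion.** The concern holds and should be fixed. The boundaries and the calculations at 30 subjects are correct; the error is to present those results as the performance of a design in which the strata share 30. If both strata enrol under the cap, both tables overstate the chance that the stratum's own rule stops the study under excess mortality. The stratum with 15 or fewer subjects is overstated by at least 23.6 points at its worst tabulated rate. At an assumed 15/15 split, the gap at or above the anticipated rates is about 6 to 24 points in each table. False stops within a stratum are overstated too, by 5.6 points (ring/band at 10%) and 6.6 points (MAC at 30%), while the whole-study false-stop chance is unreported.

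These figures assume that the boundary is checked after each subject, as the match at N = 30 supports. The study-level figures also assume independent strata.

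**What to change.** Keep the priors and the boundaries. Then:

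1. Restate both performance tables (proportion stopped, average subjects, average deaths) at stratum sizes that sum to 30, for example 10/20, 15/15 and 20/10.
2. Add the probability that either boundary is hit at the anticipated rates, with only one stratum in excess, and with both in excess.
3. Replace the two sentences claiming a high chance of stopping above 10% and above 30% with the recomputed figures.
4. Describe each prior as 6 pseudo-subjects: 20% of 30, 40% of 15.
5. Reconcile Section 10.1, where the sample may be increased, with Section 10.3, where "the total treated within both strata combined will not exceed 30". If growth beyond 30 is intended, the tables should cover it.

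The cost is a short simulation, two restated tables and a few reworded sentences. Boundaries, enrolment and conduct do not change. The stated protection in each stratum will look less favourable than it does now.

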10.3.1 Stopping Rules for valve-in-ring and for valve-in-band stratum

The study will be monitored to ensure that the mortality with 30-days after the procedure does not substantially exceed an anticipated rate. We anticipate the rate of 30-day mortality is 10% or less and determine the stopping rule by a Bayesian approach 25 . The stopping boundary is reached if the posterior probability that the 30-day mortality rate exceeds 10% is at least 90%. We take our prior distribution to be a beta distribution so that our prior clinical opinion is worth 20% of the weight we will place on the new study data, which gives the prior parameters a = 0.6, b = 5.4. Hence when we make decisions about stopping the study, the data from the study will dominate over the prior opinion.

The following table summarizes the threshold numbers for the stop rule boundary, which would lead to a recommendation to stop the study due to the excess 30-day mortality.

Number of subjects in the stratum	Stop if the number of deaths within 30 days reaches
2-4	2
5-10	3
11-17	4
18-24	5
25-30	6

We investigated the performance of the above stopping rule by a simulation study. In each simulation run, we generated a study with 30 independent Bernoulli trials, each with a true certain 30-day mortality, and compared these outcomes with the above stopping boundary to determine whether the study was stopped. We repeated the simulation 100,000 times and computed the proportion of stopped studies using the above stopping rule. The following table summarizes the performance of this stopping rule:

True 30-day mortality rate	5%	10%	15%	20%	25%	30%	35%	40%
Proportion of Stopped Studies	2.9%	16.9%	42.1%	68.7%	86.0%	94.9%	98.6%	99.7%
Average number of subjects	29.4	27	22.8	17.9	13.8	10.6	8.2	6.6
Average number of 30-day mortality	1.5	2.7	3.4	3.6	3.4	3.2	2.9	2.7

These simulation results suggest that our stopping rule has a low probability stopping a study when the true 30-day mortality rate is 10% or less, and the probability of stopping a study is high when the true 30-day mortality rate exceeds 10%. There, we believe that our Bayesian stopping rule for 30-day mortality has satisfactory statistical properties.

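### The closing sentences of 10.3.1 and 10.3.2 overstate the mortality stopping rule: at the first tabulated rate above the anticipated one it stops only 42.1% (ring/band) or 38.9% (MAC) of the time

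*Combined protocol and SAP*

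**What the plan says.** Sections 10.3.1 (valve-in-ring and valve-in-band) and 10.3.2 (valve-in-MAC) have the same structure. Each opens with the aim of ensuring that 30-day mortality does not exceed the anticipated rate by a substantial amount. In ring/band, "We anticipate the rate of 30-day mortality is 10% or less"; in MAC the anticipated rate is 30% or less. The ring/band boundary is reached when "the posterior probability that the 30-day mortality rate exceeds 10% is at least 90"%, under a beta prior, "which gives the prior parameters a = 0.6, b = 5.4". The MAC rule applies the same 90% criterion to 30%, with a = 1.8 and b = 4.2.

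Performance was simulated for a full stratum: "we generated a study with 30 independent Bernoulli trials, each with a true certain 30-day mortality". Each section then prints a table of the proportion of studies stopped and interprets it. For ring/band, "the probability of stopping a study is high when the true 30-day mortality rate exceeds 10"%. For MAC, "the probability of stopping a study is high when the true 30-day mortality rate exceeds 30"%. From this each section infers that the rule is adequate; in 10.3.2, "we believe that our Bayesian stopping rule for 30-day mortality has satisfactory statistical properties".

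Section 10.3 adds that although boundaries are given for up to 30 subjects per stratum, the two strata together will not exceed 30.

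**The concern.** The opening aim concerns substantial excess. The closing sentence drops that qualifier and ties a high stopping probability to any rate above 10% or 30%. The table above each sentence contradicts it at the first step: at 15% in ring/band and at 35% in MAC, fewer than half of the simulated studies stop. The plan gives no numerical meaning for *high*, but a probability below one half does not fit the word.

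The endpoint is 30-day death in a single-arm study, and these are the only numerical boundaries in the monitoring plan. Someone relying on the summary sentence would credit the rule with more sensitivity to moderate excess mortality than it has.

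**Working it through.** **1. Inputs.** Priors Beta(0.6, 5.4) and Beta(1.8, 4.2), reference rates p0 = 0.10 and 0.30, the 90% posterior criterion, the two boundary tables and the two performance tables, all from 10.3.1 and 10.3.2. The combined cap of 30 is from 10.3.

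**2. Boundaries.** After n subjects with x deaths the posterior is Beta(a + x, b + n − x). The boundary c(n) is the smallest x with Pr(p > p0) ≥ 0.90. For example, in ring/band, 2 deaths among 4 give Beta(2.6, 7.4) and Pr(p > 0.10) = 0.901, so the rule stops. Two deaths among 5 give Beta(2.6, 8.4) and 0.875, so 3 are needed. Repeating this for n = 1 to 30 reproduces both printed boundary tables at every n.

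**3. Stopping probabilities.** This is an exact version of the plan's simulation. Let f(n, d) be the probability of having treated n subjects with d deaths without having stopped. Then

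g(n, d) = f(n − 1, d)(1 − p) + f(n − 1, d − 1)p.

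If d ≥ c(n), g(n, d) is added to the stopping probability. Otherwise f(n, d) = g(n, d). The sum runs to n = N, with N = 30 as in the plan.

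| Ring/band: true rate | Printed | Exact |
|---|---|---|
| 5% | 2.9% | 2.8% |
| 10% | 16.9% | 17.1% |
| 15% | 42.1% | 42.6% |
| 20% | 68.7% | 68.3% |
| 25% | 86.0% | 86.0% |
| 30% | 94.9% | 95.0% |
| 35% | 98.6% | 98.5% |
| 40% | 99.7% | 99.7% |

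| MAC: true rate | Printed | Exact |
|---|---|---|
| 20% | 3.9% | 3.8% |
| 25% | 10.2% | 10.1% |
| 30% | 21.8% | 21.8% |
| 35% | 38.9% | 38.9% |
| 40% | 58.5% | 58.6% |
| 45% | 76.6% | 76.4% |
| 50% | 89.1% | 89.0% |
| 55% | 95.9% | 95.9% |

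The largest difference is 0.5 points, so the plan's figures are reproduced.

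**4. The sentence against the table.** Using the printed values, the chance of finishing without crossing is 100 − 42.1 = 57.9% at 15% in ring/band and 100 − 38.9 = 61.1% at 35% in MAC. Closer to the reference rate, the exact stopping probability is 21.6% at 11% (ring/band) and 24.9% at 31% (MAC).

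**5. Where stopping becomes likely, with 30 in the stratum.** Solving the recursion for p:

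| Stopping probability | Ring/band | MAC |
|---|---|---|
| 50% | 16.4% | 37.8% |
| 80% | 23.0% | 46.2% |
| 90% | 26.8% | 50.6% |

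**6. Effect of the shared cap.** Both strata cannot have 30 subjects. The documents give no split, so a range of assumed stratum sizes is shown.

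| Subjects in stratum | Ring/band at 15% | MAC at 35% |
|---|---|---|
| 10 | 21.7% | 17.4% |
| 15 | 26.6% | 25.7% |
| 20 | 32.4% | 30.3% |
| 30 | 42.6% | 38.9% |

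With 15 per stratum, 80% stopping is reached only at about 31.5% (ring/band) and 55.6% (MAC).

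**The case against.** The strongest reply is that nothing is hidden. The figures that contradict each sentence are printed just above it, the calculations are right, and the section's stated aim is to detect substantial excess. Against that aim the tables do well: 86.0% at 25% and 94.9% at 30% in ring/band, 89.1% at 50% and 95.9% at 55% in MAC. No rule with a continuous operating curve stops with high probability just above its reference rate, and the 80% level used above is a reviewer's convention that the plan does not set. The text says only that the simulations suggest the property, and the remark on satisfactory properties is a stated belief that the tables do not disprove.

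Most of this stands, and it makes the matter one of wording. It does not rescue the sentences, which leave out the qualifier on which the defence depends.

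A reader might infer three stronger things that the documents do not support:

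- That the boundaries are miscalculated or need redesign. They match the stated priors and criterion exactly.
- That the investigators intend to treat an uncrossed boundary as evidence of acceptable mortality. No section plans this; 10.2 plans descriptive statistics and case narratives.
- That subjects are unprotected when the boundary is not crossed. Under 10.3 the DSMB may recommend termination for safety, the sponsor and principal investigator must act on unreasonable risk after a death or serious unanticipated device effect, and each IRB may suspend. Deaths in the first year are independently adjudicated (10.2.5), and crossing the boundary itself leads only to a recommendation.

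**Conclusion.** The point holds as a misstatement in two interpretive sentences. A high stopping probability is claimed for any true mortality above 10% or 30%, while the plan's own tables give 42.1% at 15% and 38.9% at 35%. The sentences would be fair if confined to substantial excess.

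The printed figures assume 30 subjects in the stratum, outcomes checked after each subject, and independent deaths at a constant rate. Given the combined cap in 10.3 they are upper limits for each stratum. At an assumed 15 per stratum they fall to about 27% and 26%, an illustration that depends on a split the documents do not give. Section 10.1 allows the sample to be increased if needed; the upper-limit statement holds while the cap in 10.3 applies.

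The correction is worth making because it concerns the stated performance of a mortality rule and costs almost nothing. It changes no endpoint, analysis or decision rule.

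**What to change.** Leave both boundaries and both tables as they are. Replace the concluding sentence of each section with the tabulated figures, for example:

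- 10.3.1: *With 30 subjects in the stratum, the rule stops with probability 42% at a true 30-day mortality of 15%, 69% at 20% and 86% at 25%.*
- 10.3.2: *With 30 subjects in the stratum, the rule stops with probability 39% at a true 30-day mortality of 35%, 59% at 40% and 89% at 50%.*

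Add to both: *These are upper limits, because the two strata share a total of 30 subjects. Not crossing the boundary does not by itself show that mortality is at or below the anticipated rate.* If an illustration of the cap is wanted, label it as assuming 15 per stratum: about 27% at 15% and 26% at 35%, with 80% reached only at about 31.5% and 55.6%. The 30-subject values of 23.0% and 46.2% should not be presented as the study's 80% thresholds, since both strata cannot reach 30.

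The cost is a few sentences of protocol text, with no change to boundaries, subjects or procedures. The stated performance becomes less favourable.
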